3.2 Protocol Map

3.3 Primary Outcomes

The primary outcome variables will be sensitivity and specificity of the cytosponge, as compared against the gold standard of the presence of EoE as detected by upper endoscopy with biopsies.

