3.4 Secondary Outcomes

1. Agreement between cytosponge and endoscopic biopsy as measured by kappa.
2. Acceptability of cytosponge compared to endoscopy, as rated on visual analog scale.
3. Acceptability of cytosponge as measured by the Impact of Events Scale.

4 Subject Selection and Withdrawal

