6.1 Sample Size Determination

With 60 subjects enrolled for Aim 1, we will be able to detect a correlation between the Cytosponge and endoscopy eosinophil counts as low as $R = 0.40$ with a power of 0.9 and an alpha of 0.05. This sample size would also have a power of 0.8 to detect an agreement (kappa) of as low as 0.7 (compared to a null of 0.4).

We will allow for enrollment up to 150 subjects across both sites to account for any potential issues with sample quality and additional safety assessments.

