6.2 Statistical Methods

Aim 1: To test the hypothesis that the Cytosponge accurately quantifies esophageal eosinophil counts in patients with active EoE, the maximum eosinophil counts from the Cytosponge and endoscopic biopsy will be compared by calculating the Pearson coefficient of correlation. In addition, patients will be categorized as having an eosinophil count either above or below 15 eos/hpf (the current diagnostic threshold). Agreement between patients above and below this threshold for Cytosponge and endoscopic biopsy will be measured using the kappa statistic. If eosinophil counts are not normally distributed, non-parametric methods will be used. Separate analyses will be performed for patients with active EoE and patients undergoing treatment.

Aim 2: Summary statistics will be calculated to describe adverse events and the tolerability of the Cytosponge. The proportion of subjects who prefer the Cytosponge will be calculated.

We predict that the Cytosponge will be safe and well-tolerated in patients with EoE, and that they will prefer this minimally invasive method to endoscopy with biopsy. We also predict that the eosinophil counts obtained with Cytosponge will strongly correlate with the counts from endoscopy with biopsy in both patients with active EoE.

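### The primary outcome is sensitivity and specificity, but the statistical plan analyses and sizes Aim 1 only by correlation and kappa.

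*Combined protocol and SAP*

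**What the plan says.** Section 3.3 gives the primary outcome as "sensitivity and specificity of the cytosponge, as compared against the gold standard of the presence of EoE as detected by upper endoscopy with biopsies". Section 3.4 places "Agreement between cytosponge and endoscopic biopsy as measured by kappa" first among the secondary outcomes. Correlation appears in neither list.

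For Aim 1, section 6.2 states that "the maximum eosinophil counts from the Cytosponge and endoscopic biopsy will be compared by calculating the Pearson coefficient of correlation", with non-parametric methods if the counts are not normal. Patients are then "categorized as having an eosinophil count either above or below 15 eos/hpf" by each method, and kappa measures the agreement. It adds: "Separate analyses will be performed for patients with active EoE and patients undergoing treatment". The Study Summary statistics row repeats the correlation and the kappa.

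Section 6.1 gives the size: "With 60 subjects enrolled for Aim 1, we will be able to detect a correlation between the Cytosponge and endoscopy eosinophil counts". The smallest detectable correlation is put at R = 0.40, for power 0.9 at alpha 0.05. On kappa it adds: "This sample size would also have a power of 0.8 to detect an agreement (kappa) of as low as 0.7", against a null of 0.4. Enrolment may rise to 150 "to account for any potential issues with sample quality" and for further safety assessment.

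None of these places mentions sensitivity, specificity, or an interval for either. Outside section 3.3, the two measures appear for EoE only in section 1.3, as results of a 20-patient pilot: 100% and 70%.

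On population, Aim 1 in section 2, the Study Summary objective and section 6.2 all refer to patients whose EoE is active. Section 4.1 also admits patients in whom EoE is only suspected.

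**The concern.** A reader who follows section 6 obtains two statistics, neither of them primary. The primary measures are left to be inferred from a table set up for something else.

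Two consequences matter. First, kappa merges the two kinds of error. A Cytosponge that misses active disease and one that over-calls it can give the same kappa, although they mean different things for a test proposed as a substitute for endoscopy. Correlation does not measure accuracy at a threshold at all.

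Second, the powers of 0.9 and 0.8 say nothing about how precisely sensitivity and specificity will be known. Specificity was the weaker measure in the pilot. It is estimated only from biopsy-negative subjects, whom an analysis worded for active EoE would largely or wholly leave out.

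**Working it through.** **Inputs.** N = 60 and the cap of 150, R = 0.40, and kappa 0.7 against 0.4 come from section 6.1. The 15 eos/hpf threshold comes from section 6.2. The pilot values of 100% and 70% come from section 1.3 and serve only as planning values, since that pilot included patients in remission. The share of subjects who will be biopsy-positive is not given; 50%, 80% and 90% are assumed.

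**1. The plan's own figures.** Correlation, by Fisher z, two-sided 0.05: power = Φ(atanh(0.40) × √57 − 1.96) = Φ(3.198 − 1.960) = 0.892. Simulation gives 0.897. The stated 0.9 holds. Kappa 0.7 against 0.4 with N = 60: a one-sided 0.05 goodness-of-fit test has power 0.80 to 0.81 with 40-60% positive, which reproduces 0.8. The two-sided version peaks at 0.72. Section 6.1 states neither the sidedness nor the share positive for kappa, but the figure is attainable.

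**2. What kappa says about the primary outcome.** κ = (po − pe)/(1 − pe). At 50% biopsy-positive:

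- 100%/70%: po = 0.50 + 0.35 = 0.85; Cytosponge-positive = 0.65; pe = 0.5 × 0.65 + 0.5 × 0.35 = 0.50; κ = 0.35/0.50 = 0.70.
- 70%/100%: po = 0.35 + 0.50 = 0.85; Cytosponge-positive = 0.35; pe = 0.50; κ = 0.70.
- 85%/85%: po = 0.85; Cytosponge-positive = 0.50; pe = 0.50; κ = 0.70.

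Conversely, one fixed pair gives different kappas. With 100%/70% at 80% positive, po = 0.94, pe = 0.716 and κ = 0.224/0.284 = 0.79. At 90% positive, po = 0.97, pe = 0.844 and κ = 0.126/0.156 = 0.81.

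**3. Precision of specificity.** Exact (Clopper-Pearson) 95% limits for x of n: lower = Beta⁻¹(0.025; x, n−x+1), upper = Beta⁻¹(0.975; x+1, n−x). Here x is the whole number nearest 70% of the biopsy-negative subjects, with exact halves rounded down.

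| N | Biopsy-positive (assumed) | Specificity | 95% CI | Width (points) |
|---|---|---|---|---|
| 60 | 50% | 21/30 | 50.6-85.3% | 34.7 |
| 60 | 80% | 8/12 | 34.9-90.1% | 55.2 |
| 60 | 90% | 4/6 | 22.3-95.7% | 73.4 |
| 150 | 50% | 52/75 | 57.6-79.5% | 21.9 |
| 150 | 80% | 21/30 | 50.6-85.3% | 34.7 |
| 150 | 90% | 10/15 | 38.4-88.2% | 49.8 |

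Rounding the two exact halves up gives 53/75 (59.0-80.6%) and 11/15 (44.9-92.2%), which changes nothing of substance.

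**4. Precision of sensitivity.** If 100% is observed with N = 60, the intervals are 88.4-100% (30/30), 92.6-100% (48/48) and 93.4-100% (54/54), so at most 11.6 points wide. That holds only at an observed 100%. At about 90%, 27/30 gives 73.5-97.9% (24.4 points) and 49/54 gives 79.7-96.9% (17.2 points).

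**The case against.** The best defence is that the primary outcome is recoverable. Section 3.3 itself commits to the two measures and names the comparator. Section 6.2 dichotomises both methods at 15 eos/hpf, section 3.1 sets a single time point, and section 6.3 sets the population. Both proportions follow from that 2x2 table without modelling. This stands, and it rules out a stronger reading that a reader might infer: that the study cannot or will not report its primary outcome. What is missing is the analysis statement, the interval and the precision.

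A reader might also infer that the stated powers are wrong. They are not. Section 6.1 labels them as powers for correlation and kappa and does not claim that they cover sensitivity or specificity. No test or success rule is set for the primary measures, so no error rate is misstated.

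Correlation is not out of place either: Aim 1 speaks of quantifying counts, and correlation addresses that. But this shows that Aim 1 and section 3.3 pose different questions. The Study Summary methodology row does include suspected EoE, so the population problem lies in the wording of the objective and of section 6.2, not in who may enrol.

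Finally, the widest specificity intervals depend on an assumed 80% or 90% biopsy-positive. Suspected cases are eligible, so the true share may be lower.

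**Conclusion.** The mismatch is real and should be corrected before results are presented. The planned Aim 1 analysis and sizing concern one unlisted and one secondary measure, and neither answers the primary question. This is more than missing detail, because a different analysis is specified in its place and its wording for active EoE conflicts with estimating specificity.

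On size: at the pilot's 70%, the specificity interval is about 35 to 73 points wide with 60 subjects and 22 to 50 points with 150, over an assumed 50-90% biopsy-positive. Even the most favourable of these cases leaves about 22 points of uncertainty. Sensitivity should not be taken as assured: at about 90% observed with 60 subjects, its interval is roughly 17 to 24 points wide.

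The kappa result needs no pilot value. The widths rest on the assumed prevalence and on a 20-patient pilot with a different case mix. How a count of exactly 15 is classed, and which pathology review supplies the count, are details to settle but are not what makes the point hold.

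**What to change.** - **Section 6.2 and Study Summary:** state as the primary analysis the sensitivity and specificity of the Cytosponge peak count against the paired enrolment-endoscopy biopsy peak count, at the plan's 15 eos/hpf threshold, with exact 95% intervals, in the section 6.3 population. Report how many subjects have no evaluable Cytosponge count, since section 6.3 does not require one.
- **Same places:** label kappa, correlation, and follow-up or treated-patient pairs as secondary.
- **Aim 1 in section 2, section 6.2 and the Study Summary objective:** name diagnostic accuracy, and cover the section 4.1 population (suspected EoE, or diagnosed EoE with active disease).
- **Section 6.1:** label the existing powers as applying to secondary analyses. Add the interval widths for sensitivity and specificity over a stated range of prevalence. Give the achieved widths if data are already in hand, as the version 4.0 change summary suggests when it refers to available data.
- **Record:** date the change and state its timing relative to the data.

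The cost is wording only, with no new patients or measurements. The drawback is that the stated precision will look less favourable than the current power statement.

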3.4 Secondary Outcomes

1. Agreement between cytosponge and endoscopic biopsy as measured by kappa.
2. Acceptability of cytosponge compared to endoscopy, as rated on visual analog scale.
3. Acceptability of cytosponge as measured by the Impact of Events Scale.

4 Subject Selection and Withdrawal

4.1 Inclusion Criteria

1. Able to read, comprehend, and complete the informed consent form
2. Male or female subjects, age 18-80 years,
3. Suspected EoE or has a diagnosis of EoE with current active disease,

4.2 Exclusion Criteria

1. History of esophageal stricture precluding passage of the endoscope or sponge,
2. Pregnancy, or planned pregnancy during the course of the study,
3. Any history of esophageal varices, liver impairment of moderate or worse severity (Child's- Pugh class B & C) or evidence of varices noted on any past endoscopy,
4. Any history of esophageal surgery, except for uncomplicated fundoplication
5. History of coagulopathy, with INR>1.3 and/or platelet count of <75,000.
6. Current use of blood thinners such as coumadin, warfarin, clopidogrel, heparin and/or low molecular weight heparin (requires discontinuation of medication 7 days prior to and 7 days after esophagogastroduodenoscopy [EGD] and Cytosponge administration, aspirin use is OK).
7. Are allergic to local anesthetics such as lidocaine (these subjects may opt not to receive the optional lidocaine gargle prior to the Cytosponge administration and still be eligible).
8. Have not fasted the night before administration of the Cytosponge.
9. History of perforation.

4.3 Subject Recruitment and Screening

Potential subjects will be identified prior to or during their GI clinic or procedure visits at their enrolling institutions. All subjects will be screened and enrolled using EC/IRB-approved and HIPAA compliant methods.

An investigator, study coordinator, or other qualified personnel will obtain written informed consent prior to any study procedures. Potential subjects will have an opportunity to carefully review the consent form. The details of the study will be reviewed verbally, and all questions will be answered to the satisfaction of the patient. Only adults with the ability to consent will be eligible for enrollment in this study. After the subject signs the consent, a copy of the signed consent will be provided to the subject. Once written consent has been obtained, the coordinator will collect demographic and historical information from the patient pertaining to history esophageal conditions and procedures received.

The consent process will be documented by the coordinator in the patient's study file.

4.4 Early Withdrawal of Subjects

Subjects will be considered to have completed the study after completion of the last study visit (follow-up phone call). Subjects may be withdrawn prior to this for any of the following reasons:

- Death, or
- Lost to Follow-Up, or

- Withdrawal of consent, or
- Discontinuation by the investigator.

Documentation must be maintained at the site for any subject withdrawals. Subjects unable to complete Cytosponge administration will be withdrawn from the study (discontinued by investigator). Three attempts at contact using two different methods are required prior to determination that the subject is lost to follow-up. Attempts at contact must be with certified letters OR documented telephone contact. If a subject is withdrawn prior to completion of the study, the site should complete and submit a change of status case report form. See section 8.3 for additional information on case report forms. Subjects who withdraw after completion of the initial Cytosponge administration will not be replaced. Withdrawn subjects will not be followed, unless they have an active adverse event (AE) at the time of withdrawal. Subjects withdrawn while experiencing an adverse event will be followed until resolution of the AE.

5 Study Procedures

Assessment	Screening/Enrollment Visit	Follow-Up Phone Call (7 days +/- 2 days after Enrollment)	Follow-Up Cytosponge Administration ¹	Follow-Up Phone Call (7 days +/- 2 days after each follow-up Cytosponge)
Informed Consent Form	X			
Demographics	X			
Medical History	X			
Inclusion/Exclusion Criteria	X			
Cytosponge Administration	X		X	
Routine Care Endoscopy with Biopsy	X ²		X ²	
Visual Scale	X ³	X	X ³	X
Impact of Events Scale		X		X
Procedure Preference and Acceptability Questionnaire		X		X
Adverse Events⁴	X	X	X	X

¹ After enrollment, if subjects receive treatment for their EoE and return to the enrolling site for an upper endoscopy as part of their standard of care, then subjects will be asked to repeat the Cytosponge procedure prior to each follow-up standard of care endoscopy.

²Routine care biopsies should be taken during the endoscopy following the Cytosponge as this is considered standard of care for the target population. No research-specific biopsies will be obtained during the procedure.

³ The VAS should be administered immediately following completion of the Cytosponge and prior to the upper endoscopy.

⁴Only those events potentially related to participation in this research study must be reported. See section 7.2 for definition of a reportable adverse event.

5.1 Screening/Enrollment

During screening/enrollment, eligibility is assessed and those eligible and interested in participating are consented on the study. Once consent is obtained, subjects will undergo administration of the Cytosponge, complete a questionnaire and proceed with routine care upper endoscopy immediately following completion of the Cytosponge in which biopsies are taken for clinical purposes and sent to pathology.

5.1.1 Assessments

The following will be completed during the screening/enrollment visit:

- Eligibility review

- Informed consent
- Cytosponge administration
- Visual Analog Scale
- Adverse event assessment
- Routine care upper endoscopy with biopsy
- Enrollment Case Report Form (CRF): This captures demographics including race, ethnicity, gender, and year of birth, relevant EoE medical history including documentation of endoscopic procedures received to date as well as pathology findings and endoscopic history related to current diagnosis.

5.1.2 Consenting Procedure

If a subject is screened eligible and interested in the study, then the subject will be consented on the study prior to any study procedure. Written informed consent will be obtained by qualified study personnel. Documentation of the consent process will be maintained in the subject's research record.

Subjects will be given ample time to review the consent document and ask any questions they may have. A copy of the written consent form will be provided to the subject and the original maintained in the subject's research record.

If subjects meet all inclusion and none of the exclusion criteria and consent to the study, then they will be enrolled in the study. Subjects will be assigned a unique subject code. Each institution will be provided a list of subject codes to use.

5.1.3 Cytosponge Administration

The Cytosponge™ device (referred to hereafter as the "Cytosponge") will be supplied by Covidien GI Solutions to the participating sites. Study sites will be responsible for storage and accountability of the device. The Cytosponge lifetime/use by date will be confirmed on the product packaging. The device received FDA 510(k) clearance on November 26, 2014 (K142695). The Cytosponge device consists of a spherical 3.0 cm diameter reticulated polyester foam compressed and encapsulated in a standard vegetarian capsule (size 00).

Subjects will undergo administration of the Cytosponge™ according to the IFU. Briefly, subjects will be placed in the seated position and will swallow the capsule with 150 – 250 mL of water. Additional water may be used if necessary. The sponge is attached to a length of suture material which passes out through the capsule. The suture is affixed to a retainer card which is held by the subject or administrator to prevent inadvertent swallowing of the suture. The string is to be held without tension as peristalsis and gravity advance the capsule into the stomach.

The capsule dissolves in the stomach, allowing the sponge to expand to its full size. Seven minutes and 30 seconds to ten minutes after ingestion, the sponge is then withdrawn by gentle traction on the suture, collecting cells from the lining of the esophagus in passing.

After retrieval, the string is cut and the retrieved foam sphere containing the cytological specimen is immersed in fixative and stored refrigerated (1° to 12°C [34° to 54°F]) until shipped. Samples will be shipped in batches to the Mayo Clinic for initial processing, then batch shipped to the [name] lab in Cambridge for additional analysis. On arrival at the lab, the fixative is spun in a centrifuge, and the pelleted cells are embedded in paraffin using standard techniques. The blocks are sectioned and stained and processed with routine H&E staining.

If a subject fails to swallow the Cytosponge, the subject will be asked to swallow again. Subjects who are willing to try again will be asked to wait 5 minutes before the Cytosponge is presented to them again. Subjects will be able to try up to three times before they are classified as "Cytosponge swallowing failure" and discontinued by the investigator.

5.1.4 Routine Care Endoscopy with Biopsy

After Cytosponge administration is complete, subjects will undergo routine care upper endoscopy, with assessment of EoE, and biopsy. During this exam, endoscopic features of EoE will be recorded, including rings, furrows, white plaques, decreased vascularity, and strictures. The severity of the endoscopy findings will be measured using the recently validated EREFS scoring system.²³ Four esophageal biopsies will be taken both from the distal (5 cm above the gastro-esophageal junction) and proximal (15 cm above the gastro-esophageal junction) esophagus as part of their standard of care for EoE. The clinical tissue biopsies will undergo standard processing and H&E staining at the home institution, with assessment by expert gastrointestinal pathologists.

5.1.5 Adverse Event Assessment

Subjects should be assessed for any adverse events that occur before, during, or after Cytosponge administration. Only those events that are potentially related to participation in this research study must be reported to the lead site. See section 7.2 for the definition of a reportable adverse event. Sites are responsible for following local IRB/EC guidelines for reporting adverse events to their local IRB/EC.

5.2 Follow-Up Phone Call

Subjects will be contacted 7 days (+/- 2 days) following the Cytosponge and upper endoscopy procedures. During this phone call, adverse events will be assessed and subjects will complete questionnaires.

5.2.1 Assessments

The following data will be collected from subjects during the follow-up phone call:

- Visual Analog Scale
- Impact of Events Scale
- Procedure Preference and Acceptability Questionnaire
- Adverse event assessment
- Follow-Up Case Report Form (CRF): This captures relevant information for questionnaire completion and assessment of adverse events.

5.2.2 Impact of Events Scale

The impact of events scale will be completed with the subject during the follow-up phone call and measures subjective distress related to administration of the Cytosponge.

5.2.3 Procedure Preference and Acceptability Questionnaire

The procedure preference and acceptability questionnaire will be completed with the subject during the follow-up phone call. This assessment collects subject preference for the Cytosponge or traditional upper endoscopy as well as willingness to undergo the procedure again.

5.2.4 Follow-up Phone Call Adverse Event Assessment

During the follow-up phone call, subjects should be assessed for any adverse events that have occurred since administration of the Cytosponge. Only those events that are potentially related to participation in this research study must be reported. See section 7.2 for the definition of a reportable adverse event. Sites are responsible for following local IRB/EC guidelines for reporting adverse events to their local IRB/EC.

5.3 Follow-Up Cytosponge Administration

After enrollment, if subjects receive treatment for their EoE and return to the enrolling site for an upper endoscopy as part of their standard of care, then subjects will be asked to repeat the Cytosponge procedure prior to each follow-up standard of care endoscopy.

Patients will be followed and tissue will be assessed over time with both Cytosponge and routine care endoscopy; samples will be taken at up to 6 time points.

